2.5.2 Statistical hypothesis, model, and method of analysis

The time-to-first treatment emergent AE will be considered from the start of study treatment for Study A2315 only and the clinical study report will be based solely on the data from Study A2315.

The primary variable will be analyzed by a Cox regression model stratified by randomization stratum (but not by region):

- patients on QAW039 150 mg once daily treatment in Studies QAW039A2307, QAW039A2314,
- patients on QAW039 450 mg once daily treatment in Studies QAW039A2307 and QAW039A2314,
- patients on placebo in Studies QAW039A2307 and QAW039A2314
- patients on QAW039 150 mg once daily treatment in Studies QAW039A2316 and QAW039A2317,
- patients on placebo in Studies QAW039A2316 and QAW039A2317,
- patients who have not previously participated in a study of QAW039,

and treatment group, severity of asthma (GINA treatment steps 3, 4, and 5), and region as fixed class effects.

Hazard ratios comparing QAW039 450 mg once daily, QAW039 150 mg, once daily, and placebo treatments with regard to time to first treatment emergent AEs and their corresponding 95% profile likelihood confidence intervals (CIs) will be presented. Time to first treatment emergent SAEs and time to first treatment emergent AEs leading to study treatment discontinuation, will be analyzed in a similar fashion.

If the model does not converge, then the primary variable will be analyzed similar to the primary analysis but after removing stratification factors from the model. Hence in case of non-convergence, primary variable will be analyzed by a Cox regression model having treatment group, severity of asthma (GINA treatment steps 3, 4, and 5), and region as fixed class effects. If then also the model does not converge the variable will be analyzed after removing region as a fixed class effect in the model. If the resulting model also fails to converge then the variable will be analyzed considering only treatment group as a fixed class effect in the Cox regression model. [Efron's](#) method for handling ties will be used.

Summary statistics for the primary variable(s)

Ascending Kaplan-Meier curves will be constructed by treatment arm on overall population and by source of patients. The number of subjects with an event, number of subjects remaining at risk in the treatment group, estimate of the event rate and its estimated standard error, as estimable, will be provided for each treatment group. Median time to event and quartiles including 95% confidence intervals will be summarized as well.

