6.2 Patient demographics/other baseline characteristics

The following demographics and baseline characteristics will be collected on all patients:

- Age
- Gender
- Race and ethnicity
- Height
- Weight
- Body mass index (BMI)
- Duration of asthma
- Number of exacerbations in prior year
- Atopic Y/N (RAST/ImmunoCap)
- Smoking history
- Reversibility (demonstrated or historical)
- FEV1
- OCS use Y/N
- Participation in a prior Phase 3 study of QAW039
- [REDACTED]
- Relevant medical history/current medical condition present before signing informed consent. Where possible, diagnoses and not symptoms will be recorded.

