2.3 Patient disposition, demographics and other baseline characteristics

Patient demographics and baseline characteristics including age, sex, race, ethnicity, height, weight, body mass index (BMI), relevant medical history, smoking history, asthma duration, background therapies, pre- and post-bronchodilator FEV1, [REDACTED], percent predicted FEV1, [REDACTED], number of exacerbations in the previous year prior to screening will be summarized by treatment group for the SAF. Categorizations of age will include the categories of <18 years, >=18- <65 years and >=65 years of age. For rollover patients, summaries mentioning the number of patients who were adolescents (< 18 years age) at the start of the previous Phase 3 study but are adults (>= 18 years age) at the start of study A2315 will also be presented.

For rollover patients, relevant medical histories and adverse events that started and stopped in the prior phase 3 study will be recorded in Medical History CRF page of this study per investigator's judgement. Ongoing AEs in the prior phase 3 study will be recorded in Prior Study Adverse Event Outcome CRF page of this study and considered as medical history.

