2.5 Analysis of the primary objective

2.5.1 Primary endpoint

Primary endpoints for the study are:

Treatment Period 1:

- Time-to-first treatment emergent adverse events (AEs);
- Time-to-first treatment emergent serious adverse events (SAEs); and
- Time-to-first treatment emergent AE leading to discontinuation from study treatment.

of QAW039 (150 mg once daily and 450 mg once daily), compared with placebo in patients with moderate-to-severe asthma receiving SoC asthma therapy.

Treatment Period 1 and Treatment Period 2 combined:

- Time-to-first treatment emergent adverse events (AEs);
- Time-to-first treatment emergent serious adverse events (SAEs); and
- Time-to-first treatment emergent AE leading to discontinuation from study treatment.

of QAW039 (150 mg once daily and 450 mg once daily), compared with placebo in patients with moderate-to-severe asthma receiving SoC asthma therapy.

As this study has been early terminated, the primary endpoint will be analyzed in the way of combined treatment period 1 and treatment period 2. Treatment emergent AEs are defined as adverse events (including asthma exacerbations), starting on or after the day of the first intake of study drug in this study and until the earlier date out of: date of last intake of study drug +7 days (30 days in the case of a serious AE) and final visit.

Any AEs that started during the study after informed consent and before the time of the first intake of study drug will be classified as a prior AE and not classified as treatment emergent AE. The time-to-first treatment emergent AE is defined as the time to the occurrence of an AE from the treatment start date, and computed as time to AE=AE start date – treatment start date +1 day. As a general rule of censoring, patients who either completed the study or discontinued

treatment prematurely or continued treatment and without the event of interest will be censored at the minimum out of the dates of last medication intake + 30 days, final visit date, and date of death. Time-to-first treatment emergent SAEs and time-to-first treatment emergent AEs leading to discontinuation from study treatment are defined in a similar manner as time-to-first treatment emergent AE.

The definition and rationale for the estimand for the primary endpoint are given in [Table 2-1](#). The statistical strategy to handle each intercurrent event is described in more detail in [Section 2.5.3](#).

Table 2-1 Summary of estimand for the primary endpoint

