While no formal hypothesis testing is foreseen for the primary safety objectives, if both QAW039 doses have a 50% relative hazard increase for treatment emergent events, compared with placebo, then there will be approximately > 99%, 94% and 38% power that the two-sided 95% confidence interval not adjusted for multiplicity for one of the two QAW039 doses would exclude no effect for the primary safety variables of time-to-first treatment emergent AE, time-to-first treatment emergent SAE, and time-to-first treatment emergent AE leading to study treatment discontinuation analyzed across Treatment Period 1 and Treatment 2 combined, respectively. The power was estimated using 10,000 simulations based on 1,570 patients being randomized into the current study. In addition, the sensitivity of the power is further assessed for different scenarios of sample size (1470 patients and 1670 patients). This power will be higher, if more patients are randomized (e.g., due to additional new patients being enrolled) or more patients completing prior Phase 3 studies of QAW039 elect to participate in the current study.

The underlying assumptions for the power simulations were an exponential censoring rate in the placebo group of 0.22 and of 0.16 in the QAW039 treatment groups. The assumptions on the exponential event rate in each treatment group are shown in [Table 3-1](#). These assumptions are based on the, DREAM ([Pavord et al. 2012](#)) and MENSA ([Ortega et al. 2014](#)) trials, as well as a QAW039 Phase 2 study in moderate-to-severe asthma. The detailed power calculations are shown in the [Table 3-2 and Table 3-3](#).

Table 3-1 Assumed placebo event rates for power calculations

Endpoint	Previous study patients were enrolled in or new patients	Assumed exponential event rate (per patient-year)
Rate of AEs	QAW039A2316/ QAW039A2317	3.01

	QAW039A2307/ QAW039A2314	2.86
	New patients	2.86
Rate of SAEs	QAW039A2316/ QAW039A2317	0.07
	QAW039A2307/ QAW039A2314	0.24
	New patients	0.24
Rate of AEs leading to study treatment discontinuation	QAW039A2316/ QAW039A2317	0.03
	QAW039A2307/ QAW039A2314	0.03
	New patients	0.03

Table 3-2 Power (%) for a non-multiplicity adjusted confidence interval to exclude no-difference versus placebo for the primary safety variables

Primary Endpoint	Treatment Period	QAW039 150 mg versus placebo	QAW39 450 mg versus placebo	Both QAW039 150 mg and 450 mg versus placebo	One of the two QAW039 doses versus placebo
Time-to-first AE	1	>99	>99	>99	>99

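### The primary Cox models for first AE and first SAE leave out the prior-year exacerbation count; adding it is a cheap gain in precision if the count is prognostic

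*SAP*

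**What the plan says.** SAP 2.5.2, matching Protocol 9.4.2, stratifies the Cox model by the six randomization strata (prior study and prior treatment, or new patient), "and treatment group, severity of asthma (GINA treatment steps 3, 4, and 5), and region as fixed class effects". Results are hazard ratios, and "95% profile likelihood confidence intervals (CIs) will be presented".

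Protocol 6.2 lists "Number of exacerbations in prior year" among the baseline characteristics collected on all patients. Its only stated use is descriptive: SAP 2.3 says "number of exacerbations in the previous year prior to screening will be summarized by treatment group for the SAF".

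On the endpoints, SAP 2.5.1 opens its definition with "Treatment emergent AEs are defined as adverse events (including asthma exacerbations". Protocol 6.4.2 defines a severe exacerbation mainly by hospitalization or asthma death, and both are seriousness criteria in Protocol 7.2.1.

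For rollover patients, SAP 2.1.1.3 takes variables other than age, laboratory values, vital signs and ECG from the prior-study baseline. Protocol Table 6-1 marks exacerbation history at Visit 1 for new patients only.

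**The concern.** Past exacerbations are a natural predictor of future ones, and future ones feed the first-AE and first-SAE endpoints. The model's existing terms separate patient sources, treatment step and region. Within a source they leave patients with very different exacerbation histories together. The roughly 570 new patients, for example, form one stratum, and no entry criterion sets a required prior-year count.

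If the count is prognostic within strata, leaving it out has two effects:

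- A true hazard ratio above 1 is estimated somewhat closer to 1 than the ratio among patients with the same history, with less power.
- Chance imbalance against a placebo arm of about 224 goes uncorrected, and the baseline table could show an imbalance to which the plan has no pre-specified response.

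In a harm comparison, lost precision leans toward reassurance.

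**Working it through.** **Inputs from the plan (SAP Section 3, Tables 1-1 and 3-1).** N = 1570 (1000 rollover, 570 new). Placebo SAE rate per patient-year is 0.24, or 0.07 for A2316/A2317 rollovers. Censoring rate is 0.22 on placebo and 0.16 on active. Follow-up is 1 or 3 years. The effect is stated as "if both QAW039 doses have a 50% relative hazard increase for treatment emergent events, compared with placebo", so HR = 1.5. Power means that the "two-sided 95% confidence interval not adjusted for multiplicity for one of the two QAW039 doses would exclude no effect".

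**Assumed, because the documents are silent.** 300 of the 1000 rollovers come from A2316/A2317 (200 and 400 also tried), with equal prior-study arms. The count's distribution and prognostic strength are also assumed.

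**Step 1: reproduce the plan.** Simulation with six strata, Table 1-1 ratios, exponential events and censoring, a stratified Cox model and likelihood-ratio tests (equivalent to the profile interval excluding 1); 3,000 runs. GINA step and region were not simulated. Figures are 150 mg / 450 mg / both / at least one dose.

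- SAE, one year: 64/64/53/75% against the stated 65/65/54/76%.
- SAE, three years: 90/91/86/95% against the stated 89/89/84/94%.

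Agreement is within about 2 points. Other rollover splits move SAE power by about 2 to 3 points.

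**Step 2: add a prognostic count.** Two separate simulations were run, each with conditional HR 1.5.

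- Simulation A: truncated Poisson count; hazard multiplied by 1.35, 1.65 or 2.0 per SD (log-hazard SD 0.3, 0.5, 0.7); Wald intervals; 1,500 runs. Its one-year power sits below the plan's 65%, so I use its differences, not its levels.
- Simulation B: counts 0 to 4 with probabilities .15/.25/.30/.15/.15; hazard multiplied by r = 1.2, 1.5 or 2.0 per extra exacerbation, with the mean placebo rate held at the plan's value; likelihood-ratio tests; 2,000 runs. The SD of the count is √(5.20 − 1.90²) = 1.26, so the log-hazard SD is 1.26 × ln r = 0.23, 0.51, 0.87.

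SAE power per dose (%), planned model → model with count (for B, 150 mg; 450 mg):

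| Strength | A, 3 years | B, 3 years | A, 1 year | B, 1 year |
|---|---|---|---|---|
| weak | 88→89 | 89.8→90.6; 90.2→90.6 | 60→62 | 64.9→65.1; 65.8→66.2 |
| moderate | 84→88 | 84.6→89.3; 85.7→90.5 | 57→61 | 59.8→62.3; 59.1→62.8 |
| strong | 75→87 | 69.1→84.8; 68.9→84.2 | 51→59 | 51.2→61.2; 52.7→61.0 |

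Gains over three years are about 0–1, 4–5 and 12–16 points (the top figure is 84.8 − 69.1 = 15.7). Over one year they are about 0–2, 3–4 and 8–10. The three-year hazard ratio from the planned model averages 1.48, 1.46 and 1.43 (A) or 1.49, 1.47 and 1.39 (B).

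**Step 3: first AE and discontinuation (B, three years, Wald).** For first AE the planned model gives HR 1.47, 1.41 and 1.33 at r = 1.2, 1.5 and 2.0. Power stays near 99% up to r = 1.5 and is about 92% at r = 2.0. For AE-related discontinuation, adjustment changes per-dose power by no more than about 1 point at r = 1.2 and 1.5. Expected placebo events there are few: 224 × (0.03/0.25) × (1 − e^(−0.25×3)) ≈ 14.

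**Step 4: no treatment effect.** With HR = 1 the planned SAE model gives an average HR of 1.00. It excludes 1 in 5.1% and 5.4% of runs at r = 1.5, and in 4.6% for each dose at r = 2.0.

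**Step 5: chance imbalance.** With 3:3:1 allocation the arms are about 673, 673 and 224. The 95% range for a dose–placebo difference in mean count is 1.96 × √(1/224 + 1/673) = 0.15 SD. Multiplied by a log-hazard SD of 0.3, 0.5 or 0.7, this is 0.045, 0.076 or 0.106, which moves the hazard ratio by about 5%, 8% or 11%. The interval already allows for this random error; adjustment removes it.

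**The case against.** The strongest reply is that this is a modelling preference. Protocol and SAP pre-specify the same executable model, it keeps its error rate, and "While no formal hypothesis testing is foreseen for the primary safety objectives". That stands: the plan contains no error here.

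Several further points also stand and reduce the size.

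- For about 1000 of 1570 patients the count describes the year before the parent study, so it is older and probably less predictive.
- Source strata already separate SAE rates of 0.07 and 0.24, and GINA step captures some severity. The simulations treat all the assumed spread as residual.
- SAEs cover every hospitalization and medically significant event. The documents do not say what share are exacerbations, so a strong effect on all-cause SAEs is a demanding assumption.
- SAP 2.5.1 records early termination. The one-year gains may be nearer the mark than the three-year ones, and the stated 89% no longer describes this study.

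A reader might infer that the planned hazard ratio is biased toward 1. The documents do not support that. The gap is non-collapsibility: ratios conditional and not conditional on the count are different quantities, the gap vanishes at HR = 1, and SAP Table 2-1 does not define its hazard ratio as conditional on exacerbation history. A reader might also infer that leaving out the count undermines the independent-censoring assumption in SAP 2.5.3. That would need the count to drive both stopping and events, which nothing in the documents shows; the simulations used censoring unrelated to the count.

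None of this shows that adjustment would do harm, or that another part of the visible plan already uses the count.

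**Conclusion.** The point holds as an inexpensive improvement. The planned analysis is valid, but it leaves unused a listed baseline value that bears directly on two of the three primary variables. The benefit is conditional on the count being prognostic within strata. For SAE power per dose at HR 1.5 it is negligible if the count is weak, about 4–5 points over three years (3–4 over one) if moderate, and 12–16 (8–10 over one) if strong. These figures rest on an assumed count distribution, an assumed range of strengths and an assumed split of the rollovers. The actual gain is likely to be at the lower end. A claim that power has been lost, or that the stated power is wrong, would go beyond the documents, which give no prognostic strength.

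**What to change.** Before database lock, add to SAP 2.5.2 the prior-year exacerbation count in categories 0, 1, 2, and 3 or more as a fixed class effect in the Cox models for first treatment emergent AE and first treatment emergent SAE. Use the baseline in SAP 2.1.1.3, with a missing category if needed. State that this term is dropped first if a model does not converge, ahead of the existing sequence. Leave the model for AEs leading to discontinuation as it is, because events are few. Confirm that the rollover count can be drawn from the parent studies, since Table 6-1 does not collect it again. If those making the change have already seen results by arm, present the adjusted model as a named sensitivity analysis instead.

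The cost is one sentence in the SAP, three extra parameters (four with a missing category), and a slightly different model for one of the three primary variables.

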5.3 Treatment assignment and randomization

At Visit 201, all eligible patients/subjects will be randomized via Interactive Response Technology (IRT) to one of the treatment arms. The investigator or his/her delegate will contact the IRT after confirming that the patient fulfills all the inclusion/exclusion criteria. The IRT will assign a randomization number to the patient, which will be used to link the patient to a treatment arm and will specify a unique medication number for the first package of study drug to be dispensed to the patient. The randomization number will not be communicated to the caller.

The randomization numbers will be generated using the following procedure to ensure that treatment assignment is unbiased and concealed from patients/subjects and investigator staff. A patient randomization list will be produced by the IRT provider using a validated system that automates the random assignment of patient numbers to randomization numbers. These randomization numbers are linked to the different treatment arms, which in turn are linked to medication numbers. A separate medication list will be produced by or under the responsibility of Novartis Drug Supply Management using a validated system that automates the random assignment of medication numbers to packs containing the investigational drug(s).

Note: Enrollment to patient strata may be restricted by the Sponsor prior to the end of overall recruitment in order to achieve the desired distribution in the trial population.

The randomization scheme for patients/subjects will be reviewed and approved by a member of the Randomization Group.

Details of randomization scheme

Overall, there is an approximately 85% chance patients will receive QAW039 in Study A2315. For patients who participated in a prior Phase 3 study, there is at least 57% chance a patient will remain on the same QAW039 dose they received in the prior study in Study A2315.

Patients completing A PRIOR PHASE 3 STUDY OF QAW039 with 3 treatment arms (QAW039A2307 and QAW039A2314) will be randomized to treatment in Study A2315 as delineated below.

- Patients who received QAW039 450 mg once daily in a prior study will be assigned to QAW039 450 mg once daily, QAW039 150 mg once daily, or placebo in a 5:1:1 ratio.
- Patients who received QAW039 150 mg once daily in a prior study will be assigned to QAW039 450 mg once daily, QAW039 150 mg once daily, or placebo in 1:5:1 ratio.

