- Patients on placebo in a prior study will be assigned to QAW039 450 mg once daily, QAW039 150 mg once daily, or placebo in 3:3:1 ratio.

Patients completing A PRIOR PHASE 3 STUDY OF QAW039 with 2 treatment arms (QAW039A2316, QAW039A2317) will be randomized to treatment in Study A2315 as delineated below.

- Patients who received QAW039 150 mg once daily in a prior study will be assigned to QAW039 450 mg once daily, QAW039 150 mg once daily, or placebo in 2:4:1 ratio.
- Patients who received placebo in prior study will be assigned to QAW039 450 mg once daily, QAW039 150 mg once daily, or placebo in 4:2:1 ratio.

Patients who HAVE NOT PREVIOUSLY PARTICIPATED IN A STUDY OF QAW039 will be randomized to treatment in Study A2315 as follows: QAW039 450 mg once daily, QAW039 150 mg once daily, or placebo in a 3:3:1 ratio.

Treatment randomization will be stratified at the regional level.

[Table 5-1](#) shows the randomized allocation of patients into treatment groups in Study A2315.

Table 5-1 Randomized Allocation of Patients into Treatment groups

Patients completing A PRIOR PHASE 3 STUDY OF QAW039: treatment allocation in Study A2315			
Prior study	Treatment group in prior study	Randomization ratio in Study A2315	Treatment group in Study A2315
CQAW039A2307 CQAW039A2314	450 mg once daily	5 1 1	QAW039 450 mg once daily QAW039 150 mg once daily Placebo
	150 mg once daily	1 5 1	QAW039 450 mg once daily QAW039 150 mg once daily Placebo
	Placebo	3 3 1	QAW039 450 mg once daily QAW039 150 mg once daily Placebo
CQAW039A2316 CQAW039A2317	150 mg once daily	2 4 1	QAW039 450 mg once daily QAW039 150 mg once daily Placebo
	Placebo	4 2 1	QAW039 450 mg once daily QAW039 150 mg once daily Placebo
Patients who HAVE NOT PREVIOUSLY PARTICIPATED IN A STUDY OF QAW039: treatment allocation in Study A2315			
Prior study	Treatment group in prior study	Randomization ratio in Study A2315	Treatment group in Study A2315
Not applicable	Not applicable	3 3 1	QAW039 450 mg once daily QAW039 150 mg once daily Placebo

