9.4.2 Statistical model, hypothesis, and method of analysis

The time-to-first treatment emergent AE will be considered from the start of Study A2315 only and the clinical study report will be based solely on the data from Study A2315.

The primary variable will be analyzed by a Cox regression model stratified by randomization stratum (but not by region):

- patients on QAW039 150 mg once daily treatment in Studies QAW039A2307 and QAW039A2314,
- patients on QAW039 450 mg once daily treatment in Studies QAW039A2307 and QAW039A2314,
- patients on placebo in Studies QAW039A2307 and QAW039A2314,
- patients on QAW039 150 mg once daily treatment in Studies QAW039A2316 and QAW039A2317,
- patients on placebo in Studies QAW039A2316 and QAW039A2317,
- patients who have not previously participated in a study of QAW039,

and treatment group, severity of asthma (GINA treatment steps 3, 4 and 5), and region as fixed class effects.

Hazard ratios comparing QAW039 450 mg once daily, QAW039 150 mg, once daily, and placebo treatments with regard to time to first treatment emergent AEs and their corresponding 95% profile likelihood confidence intervals will be presented. The other primary variables, treatment emergent SAEs and AEs leading to study treatment discontinuation, will be analyzed in a similar fashion.

The detailed statistical analysis plan will pre-specify how strata would be pooled for analysis purposes, if this is necessary.

The same analyses will be performed based on the Treatment Period 1 data and based on the entirety of the study (Treatment Period 1 and Treatment Period 2 combined). A multiplicity adjustment for these two separate assessments is not foreseen.

Summary statistics for the primary variable

[figure not shown]

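### When the Cox model fails to converge, SAP 2.5.2 drops the randomization strata first; its last, treatment-only fallback should keep them, because 450:150 allocation differs by stratum

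*SAP*

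**What the plan says.** The primary model in SAP 2.5.2 is a Cox regression stratified by six groups defined by source study and prior treatment (new patients form one group). Treatment, GINA step and region are fixed effects.

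Non-convergence is handled in three steps:

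1. The strata go: "then the primary variable will be analyzed similar to the primary analysis but after removing stratification factors from the model". Treatment, GINA step and region stay.
2. Region goes.
3. GINA step goes, and the variable is "analyzed considering only treatment group as a fixed class effect in the Cox regression model".

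No step restores the strata.

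Protocol 5.3 and Table 5-1 set a different 450:150:placebo ratio by stratum. For A2307/A2314 it is 5:1:1 (prior 450 mg), 1:5:1 (prior 150 mg) and 3:3:1 (prior placebo). For A2316/A2317 it is 2:4:1 (prior 150 mg), while prior-placebo patients get 450 mg, "150 mg once daily, or placebo in 4:2:1 ratio". New patients are 3:3:1. The protocol states the result for patients from earlier trials: "there is at least 57% chance a patient will remain on the same QAW039 dose they received in the prior study".

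Protocol 9.4.2 adds: "The detailed statistical analysis plan will pre-specify how strata would be pooled for analysis purposes, if this is necessary". The visible SAP text contains no pooling rule, but parts of the SAP are redacted.

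**The concern.** Because the 450:150 ratio changes with prior treatment, the two dose groups are comparable by randomization only within a stratum. An unstratified treatment-only model compares a 450 mg group rich in prior-450 patients with a 150 mg group rich in prior-150 patients. If hazard depends on prior arm, that difference enters the dose-specific hazard ratios. The contrast of 450 with 150 is among the summary measures in SAP Table 2-1.

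The likeliest place for the fallback is the rarest endpoint, AEs leading to discontinuation, and early termination makes events fewer: "As this study has been early terminated, the primary endpoint will be analyzed in the way of combined treatment period 1". The planned Kaplan-Meier display would not reveal the problem, since it splits patients by source and not by prior arm: "Ascending Kaplan-Meier curves will be constructed by treatment arm on overall population and by source of patients".

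**Working it through.** **Inputs.** Ratios: Protocol Table 5-1. Placebo event rates, censoring (0.22 placebo, 0.16 active), hazard ratio 1.5 and N = 1,570 (1,000 rollover, 570 new): SAP section 3. Assumed, because the documents do not give them: the rollover split between programmes, equal prior arms unless stated, and every prior-arm hazard multiplier.

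**1. The plan's own figures.** Simulating six strata with a stratified Cox model, profile-likelihood intervals and a 750:250 split gives Period 1 power (150 mg / 450 mg / both / one of two) of:

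- SAE: 66.9/65.2/55.0/77.2, against 65/65/54/76 in Table 3-2.
- Discontinuation AE: 16.8/16.5/9.2/24.1, against 16/16/9/22.

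The design is therefore read as intended.

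**2. Confounding without strata.** Formula: mean hazard in arm a = Σ(n_s × p_sa × h_s) / Σ(n_s × p_sa), where n_s is stratum size, p_sa the allocation fraction and h_s the relative hazard. Assume 725 patients from A2307/A2314 (241.7 per prior arm), 275 from A2316/A2317 (137.5 per arm) and 570 new. Each dose arm has 1,570 × 3/7 = 672.9 patients and placebo has 224.3.

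Example: the A2307/A2314 prior-450 hazard is doubled and the base rate is equal elsewhere. That stratum puts 241.7 × 5/7 = 172.6 patients in the 450 arm and 34.5 in each other arm.

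- 450 mg: (672.9 + 172.6)/672.9 = 1.257
- 150 mg: (672.9 + 34.5)/672.9 = 1.051
- Placebo: (224.3 + 34.5)/224.3 = 1.154
- 450 versus 150: 1.257/1.051 = 1.195

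Varying the A2307/A2314 share moves that ratio. With 500 patients it is (672.9 + 119.0)/(672.9 + 23.8) = 1.137. With 900 it is (672.9 + 214.3)/(672.9 + 42.9) = 1.240.

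| Scenario (true ratio 1) | 450 vs placebo | 150 vs placebo | 450 vs 150 |
|---|---|---|---|
| Table 3-1 rates, equal prior arms, all endpoints | 1.000 | 1.000 | 1.000 |
| SAE, Table 3-1 rates, 60:40 roll-over in both programmes* | 1.013 | 0.986 | 1.028 |
| Prior-450 ×0.70, prior-150 ×0.85, both programmes | 0.988 | 1.012 | 0.976 |
| A2307/A2314 prior-450 ×1.5 | 1.048 | 0.952 | 1.100 |
| A2307/A2314 prior-450 ×2 | 1.089 | 0.911 | 1.195 |
| Prior-150 ×2, both programmes | 0.894 | 1.106 | 0.808 |

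*Prior-450 to prior-150 in A2307/A2314; prior-150 to prior-placebo in A2316/A2317.

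Discontinuation AEs have rate 0.03 in every source, so unequal roll-over alone creates no confounding there. Placebo is 1/7 of every stratum, so pooled active versus placebo is not confounded in any row. Separately, when the true SAE ratio is 1.5, dropping strata at Table 3-1 rates attenuates it slightly (1.49 to 1.47 at 750:250). That is rate heterogeneity, not allocation imbalance.

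**3. Interval coverage, 450 versus 150, discontinuation AEs** (Wald intervals, stratified versus unstratified):

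- 0.70/0.85 case: 95.1% vs 95.0% (52 weeks), 95.1% vs 94.5% (156 weeks).
- ×1.5: 96.0% vs 94.1%, 94.9% vs 90.7%.
- ×2: 95.2% vs 89.6%, 95.3% vs 81.6%.

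For 450 versus placebo, unstratified coverage never fell below 94.8%. Coverage for 150 versus placebo was not evaluated.

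**4. Does dropping strata rescue the fit?** Strata add no coefficients to a Cox model. In 27,000 treatment-only runs both models were non-finite in the same 168, with none discordant; all 168 had no placebo event, which removing strata cannot cure. A separate 1,600 runs also gave none discordant.

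With covariates still in the model the picture is mixed. Keeping GINA step, non-finite fits were 120 of 600 stratified and 50 of 600 unstratified at 26 weeks (13 and 4 of 600 at 52 weeks). With eight assumed regions plus GINA step (rate 0.03, one year), 42.0% converged stratified and 43.5% unstratified, against 99.5% for stratified treatment-only.

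**5. Cost in precision.** Simulated standard errors at 52 weeks, unstratified to stratified:

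- Versus placebo: 0.453 to 0.456 (0.456/0.453 = 1.007).
- 450 versus 150: 0.272 to 0.293 (0.293/0.272 = 1.077).

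The second follows from the design. Information per patient on 450 versus 150 is proportional to pq, where p and q are the two doses' shares of the active patients: 5/36 for 5:1, 2/9 for 2:4 and 1/4 for 3:3. The weighted mean is (483.3 × 0.139 + 275 × 0.222 + 811.7 × 0.25)/1,570 = 0.211, and √(0.25/0.211) ≈ 1.09.

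**The case against.** The strongest reply is that the harm is hypothetical and the remedy is not free.

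- **No document figure produces a material bias.** Table 3-1 rates do not vary by prior arm. The larger multipliers have no source. Rollover patients completed blinded treatment and had no serious drug-related AE (criteria 2a and 5a), which points to lower hazard after active treatment. The case of that kind, 0.70/0.85, gives 0.976 with coverage near nominal. This stands.
- **Harm and trigger pull apart.** The worst coverage is at 156 weeks, with about 150 discontinuation events, where the fallback is least likely and which early termination has made moot. SAEs are an unlikely trigger: about 371 events at 52 weeks on the SAP's rates with hazard ratio 1.5. This stands too.
- **Keeping strata can cost more than it saves for 450 versus 150.** On mean squared error it pays only if the prior-450 multiplier exceeds a value between 1.5 and 2 (52 weeks), or between 1.25 and 1.5 (156 weeks). True, but the stated objective is comparison with placebo, where the cost is under 1%.
- **At the intermediate steps the SAP's order is a real trade-off.** Removing strata does help while GINA step stays, and region is itself a randomization factor. This does not reach the last step, where removal gains nothing.

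A reader might also infer that the SAP broke a protocol promise on pooling. The documents do not support that: the protocol sentence is conditional on need, and redacted SAP text cannot be counted as absent.

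**Conclusion.** The point holds as an improvement to a contingency rule. At the final fallback the strata are removed without benefit, and the dose-specific ratios, mainly 450 versus 150, lose their randomization protection.

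Harm needs two things. The fallback must be used, and hazards must differ by prior arm (or, for SAEs, roll-over must be unequal by arm). Its size is nil at Table 3-1 rates with equal prior arms, at most 1.028 for SAEs in the 60:40 roll-over cases examined, and 1.195 for 450 versus 150 under an assumed doubling in one prior arm.

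A reader might infer that the primary analysis is biased, or that the fallback will probably be reached. Neither follows. The primary model is stratified. The SAP states no convergence criterion, so no trigger rate can be given, and a non-finite estimate in simulation is not the same as a software convergence failure. The coverage figures use Wald rather than profile-likelihood intervals. Nor does a test decision hang on this: "While no formal hypothesis testing is foreseen for the primary safety objectives" (SAP section 3).

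**What to change.** In SAP 2.5.2, answer non-convergence by removing covariates (region and GINA step, in the order the sponsor prefers) rather than the strata, so that the last fallback is a Cox model stratified by randomization stratum with treatment only. That last step is the essential change. If strata must be pooled, pool only those with the same allocation ratio: A2307/A2314 prior placebo with new patients, both 3:3:1.

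Optional additions are a stated convergence criterion and a Firth-penalized stratified fit when an arm has no event. The latter was finite in 120 of 120 simulated runs without a placebo event, and SAP 2.8.1 already uses Firth's method for its logistic model.

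The cost is one paragraph, the standard-error increases shown above (under 1% versus placebo, about 7-10% for 450 versus 150), and covariates that may be dropped earlier than now.
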